#### **6.1.3** Exploratory Objective(s)

Exploratory objectives will include the assessment of free living activity in subjects on Bavisant compared to placebo after 6 weeks of treatment using a wrist-worn actigraphy device and pharmacogenomics analysis.

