#### 11.1.3 Efficacy Analyses

# 11.1.4 Primary Efficacy Analyses

ESS mean absolute change from baseline to the end of the 6-week treatment period will be analysed with an ANCOVA model, with the baseline ESS as a covariate, region and treatment as a factor. Missing data in the 6-week ESS evaluation will be considered as a treatment failure, that is imputing the missing ESS reduction as 0. Least-squared (LS) absolute mean changes will be presented by treatment group together with their corresponding 95% confidence interval. Paired-comparisons will be performed without any multiplicity adjustment.

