# 11.1.6 Exploratory Analyses

All variables obtained with the wearable tool assessing a mean absolute or a mean relative change will follow a similar methodology as for the primary variable. Categorical variables will be described and compared between groups by means of a Chi-square test (or Fisher's exact test

Amendment 04, Final Version 1.0 07/Nov/2018 Page 81 / 142

according to corresponding applicability). Percentages and difference between treatments will be expressed with their 95% confidence interval calculated with a binomial exact method.

Both univariate and multivariate statistical methods will be used as an exploratory pharmacogenomic analysis in order to identify genetic reasons why certain people respond differently to Bavisant, to find out more information about how Bavisant works, and to generate information needed for research, development, and regulatory approval of tests to predict response to Bavisant, and to identify variations in genes related to the biological target of Bavisant.

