3.3 Exploratory Objectives

[figure not shown]
Exploratory objectives will include the assessment of free living activity in subjects on Bavisant compared to placebo after 6 weeks of treatment using a wrist-worn actigraphy.

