10.3 Exploratory Efficacy Analysis

We aim to characterise the changes in free-living activity by means of wrist-worn actigraphy. GENEActiv accelerometers are worn on the wrist and measure tri-axial acceleration with a sample

frequency of 100Hz. The device also measures temperature and light levels. The data is collected pre- and post- dosing (V3), each over a period of seven days. We aim to measure differential physical activity behaviour, and also the length and frequency of daytime sleep episodes.

The data is to be processed using the calibrated GENEActiv tracker data pre-processing package in R. We extract 12-hour daytime records and convert the accelerometer to gravity-subtracted Signal Vector Magnitudes (SVMgs), which is our measure of instantaneous physical intensity. The time-series is downsampled (100x) to one second intervals by averaging the instantaneous SVMgs across the 100 time points. The averaged SVMgs are grouped into four intensity levels groups: Sedentary (< 4.5), Light (4.5-16.5), Moderate (16.5-42), and Vigorous (> 42). These threshold boundaries may change as thresholds used in existing studies are calibrated for different populations. The summary statistics we aim to extract are bout lengths and frequencies, where a bout is a continuous episode of physical activity at a specific intensity levels band. Using paired t-tests, we aim to demonstrate a reduction in sedentary activity and an increase in light to vigorous activity in the dosed population. Using automatic changepoint detection methods (such binary segmentation methods and its extensions, with the fused lasso total variation regulariser, together with Bayesian approaches such as Dirichlet process hidden Markov models.) for detection of sleep boundary times, we also, independently of activity level measurements, aim to quantify the frequency and lengths of daytime sleep episodes.

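### SAP 10.3 tests the actigraphy activity summaries only before versus after within dosed subjects, with no placebo contrast, although the objective is a comparison with placebo

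*SAP*

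**What the plan says.** SAP 10.3 describes two recording periods: "The data is collected pre- and post- dosing (V3), each over a period of seven days". From these it derives the length and frequency of activity bouts in four intensity bands (sedentary, light, moderate, vigorous). The only test it names is: "Using paired t-tests, we aim to demonstrate a reduction in sedentary activity and an increase in light to vigorous activity in the dosed population". It names no treatment factor, covariate or placebo contrast, and does not say whether the doses are pooled. For daytime sleep episodes it plans to quantify frequency and length and names no test.

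The objective is comparative. SAP 3.3 gives it as "assessment of free living activity in subjects on Bavisant compared to placebo after 6 weeks of treatment using a wrist-worn actigraphy", and Protocol 6.1.3 agrees.

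On method, Protocol 11.1.6 says that variables "obtained with the wearable tool assessing a mean absolute or a mean relative change will follow a similar methodology as for the primary variable". Protocol 11.1.4 defines the primary method: the change is "analysed with an ANCOVA model, with the baseline ESS as a covariate, region and treatment as a factor".

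Other sections also bear on the point:
- The Protocol synopsis and Protocol 6.2.3 and 8.4.6 promise descriptive statistics by treatment group for the accelerometry.
- SAP 10.2 lists a six-week motor-function variable from the wrist device among the ANCOVA endpoints, without defining it.
- SAP 1 says the SAP leaves the protocol analysis as it is, and SAP 14 declares no changes.

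**The concern.** A change from the baseline week to the week before Visit 3 can come from the drug. It can also come from placebo response, being in a trial, wearing the device a second time, season, or regression to the mean. A paired test in dosed subjects responds to the sum of these. Protocol 7.2 makes the same argument when it justifies the placebo arm as showing the course of sleepiness under trial conditions.

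The SAP says it aims to demonstrate less sedentary and more active time. A significant paired result would easily be read as evidence of drug effect, although the test never asks whether dosed subjects changed more than placebo subjects. The error can run the other way too: an unfavourable common shift could hide a real effect. The placebo recordings will exist, because Protocol 8.4.1.15.9 offers the device to about half of all subjects without restriction by arm.

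**Working it through.** **Step 1. Compare the texts.**

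| Place | What it fixes |
|---|---|
| Protocol 6.1.3, SAP 3.3 | Question: Bavisant versus placebo at 6 weeks |
| Protocol 11.1.6 with 11.1.4 | Method for wearable change variables: similar to the primary ANCOVA (baseline, region, treatment) |
| Protocol synopsis, 6.2.3, 8.4.6 | Descriptive statistics by treatment group |
| SAP 10.2 | ANCOVA for one undefined wrist-device variable |
| SAP 10.3 | Paired t-tests in the dosed population for the bout summaries |
| SAP 14 | No changes from the protocol |

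The protocol's two statements can stand together: describe by group, and model change as for the primary variable. Neither yields a significance test confined to dosed subjects. SAP 10.3 is therefore an undeclared departure, and it does not answer the stated objective.

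**Step 2. Size (illustration only).** The plan gives no SD, effect, power or sample size for actigraphy, so there is no stated figure to reproduce.

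Inputs from the documents: about 230 randomised or 200 completed, allocation 1:1:1:1, about 50% offered the device, two-sided 0.05 (Protocol 11.1). Assumptions: everyone offered the device supplies both recordings; there is no drug effect; every arm has the same mean shift δ, in SDs of the change score.

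Numbers in the test:
- Doses pooled, from 230: 230 × 3/4 × 1/2 = 86.25, taken as 86.
- Doses pooled, from 200: 200 × 3/4 × 1/2 = 75.
- One dose arm, from 230: 230 × 1/4 × 1/2 = 28.75, taken as 29.
- One dose arm, from 200: 200 × 1/4 × 1/2 = 25.

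The paired t statistic has a noncentral t distribution with n − 1 degrees of freedom and noncentrality δ√n. For δ = 0.3 and n = 86 this is 0.3 × √86 = 2.78. The rejection rate is P(|T| > t(0.975; n − 1)):

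| n | δ = 0 | 0.1 | 0.2 | 0.3 | 0.5 |
|---|---|---|---|---|---|
| 86 (pooled) | 5% | 15% | 45% | 79% | 99.6% |
| 75 (pooled) | 5% | 14% | 40% | 73% | 99% |
| 29 (one arm) | 5% | 8% | 18% | 34% | 74% |
| 25 (one arm) | 5% | 8% | 16% | 30% | 67% |

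In a dosed-versus-placebo comparison the common shift cancels. A simulation of 20,000 trials with 75 dosed and 25 placebo subjects, using a two-sample t-test as a simple stand-in for the ANCOVA contrast, rejected in 4.9%, 4.9%, 4.9% and 4.7% of trials at shifts of 0, 0.2, 0.3 and 0.5 SD.

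**The case against.** The strongest reply has four parts.

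**Within-arm change belongs to the primary method.** Protocol 6.2.1 assesses the primary endpoint both within group and against placebo, and SAP 10.1 reports within-arm change with intervals and p-values. This stands: within-arm change may be reported. But SAP 10.1 takes it from the ANCOVA least-squares means and reports the placebo differences alongside, and SAP 10.3 lacks that second half.

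**The placebo arm is not ignored elsewhere.** SAP 7 displays the four groups separately, and SAP 10.2 puts one device variable under ANCOVA. A reader might infer that the SAP discards the placebo actigraphy data altogether; the documents do not support that. Still, the 10.2 variable is undefined. If it excludes the bout summaries, they have no placebo test. If it includes them, the SAP gives two methods for the same data.

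**The protocol is not explicit.** A reader might infer that it prescribes ANCOVA for actigraphy outright. It does so only by reference in 11.1.6, while three other places speak of description by group. This tempers the wording but gives no support to a test within dosed subjects.

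**The 79% is near the unfavourable end.** It needs pooled doses, full uptake, no dropout and a 0.3 SD shift that has no source in the documents. Only about half are offered the device, and SAP 7 adds a pooled active column for safety only. Taking 15% withdrawal off 86 leaves about 73, and the rate is 71.5%; tested by arm it is about 30% to 34%. This stands, so the figure must be read as one cell of a range.

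The criticism of the paired test also does not reach the sleep episodes, for which SAP 10.3 names no test.

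**Conclusion.** The point holds for the bout summaries. The only test SAP 10.3 names for them cannot address the stated objective, departs from the method that Protocol 11.1.6 points to, and is not declared in SAP 14. This follows from the text and needs no numerical assumption.

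The size does rest on assumptions: no drug effect, a common shift, and the uptake shown. Over shifts of 0.2 to 0.5 SD the paired test would be significant in about 40% to 99.6% of trials with doses pooled, and in about 16% to 74% by single arm, against about 5% for a placebo-controlled comparison. No single value in that range is the trial's false-positive rate.

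A reader might also infer that the trial's efficacy conclusion is at risk. It is not: this is an exploratory objective in an optional subset, and the ESS analysis does not depend on it. The correction is still worth making, because it is cheap and the placebo data will already be there.

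**What to change.** In SAP 10.3:
1. For each bout summary, make the primary ANCOVA the inferential analysis: change at Visit 3, that summary's baseline value as covariate, region and treatment as factors, each dose versus placebo with a 95% interval.
2. Take within-arm change from the same model, as SAP 10.1 does, label it supportive, and state that it will not be used to claim a drug effect. Drop the paired t-tests as the efficacy evidence.
3. Use the same model for the sleep-episode summaries if they are to be tested.
4. In SAP 10.2, say which variable the motor-function item is, or refer to 10.3.
5. If the sponsor keeps the paired tests as the efficacy evidence, declare and justify the departure in SAP 14.

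The cost is SAP wording before unblinding; no new data are needed. Two downsides should be stated. First, length and frequency in four bands give 8 summaries, and three doses make 24 unadjusted contrasts (30 if two sleep measures are added), so they should be read as exploratory. Second, precision is limited: with 25 per arm, a two-sample t-test has about 41% power for a 0.5 SD difference and 79% for 0.8 SD. Estimates with intervals will say more than p-values.

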10.4 Efficacy analysis Considerations

10.4.1 Pooling of Regions

Regions where the low number of subjects is making the statistical model questionable (<20 patients) will be merged with the closer region according to the regional location. If some of the investigative sites are able to enrol a sufficient number of subjects (≥ 20) they will not be merged with the others in the region and will be considered as an independent fixed effect region category in the model. Any required pooling will also be applied to the per-protocol population to allow a valid comparison of the study results.

10.4.2 Handling of missing data

- For primary analysis, as describes in section 9.1, post-baseline ESS will be imputed through a Multiple Imputation Jumping to Reference Model.

11 SAFETY ENDPOINTS

The safety analysis will be based on the reported adverse events and other safety information, such as clinical laboratory data and physical examination as described in the protocol.

The safety of Bavisant compared to placebo will be assessed by the evaluation of the following:

- Incidence of Adverse Events (AEs), Serious Adverse Events (SAEs), Serious and related Adverse Events and Adverse Events of Special Interest (AESIs) headache, nausea and insomnia
- Incidence of suicidal ideation (C-SSRS) findings from screening/baseline to the end of the 2-week and the 6-week treatment period and safety follow-up
- Incidence of positive psychotic symptoms (BPRS+) findings from screening/baseline to the end of the 2-week and the 6-week treatment period and safety follow-up
- Incidence of physical examination, vital signs and laboratory tests changes from normal to abnormal (haematology and biochemistry)
- Incidence of cardiovascular safety findings (blood pressure, heart rate, ECG including QT/QTc)

11.1 Analysis Sets Analysed for Safety

Safety endpoints will be evaluated in the SAF population as defined in section 6.0, and will be presented by treatment group.

12 STATISTICAL METHODOLOGY FOR SAFETY ENDPOINTS

The baseline value is defined as the last available value before the first dose of double-blind IMP taken.

The analysis of the safety variables will be essentially descriptive and no systematic testing is planned.

The observation period of safety data will be divided into 2 sub-periods:

- The pre-treatment period is defined as the time between the date of signed informed consent and the first dose of double-blind IMP.
- The on-Treatment period (TEAE period): is defined as the Date/ time from first dose of double-blind IMP.

12.1 Incidence of Adverse Events (AEs), Serious Adverse Events (SAEs), and Adverse Events of Special Interest (AESIs) such as headache, nausea and insomnia

All adverse events will be analysed and determined to be either pre-treatment or treatment-emergent. If an adverse event date/time of onset (occurrence, worsening, or becoming serious) is incomplete, an imputation algorithm will be used to classify the adverse event as pre-treatment or treatment-

emergent. The algorithm for imputing date/time of onset will be conservative and will classify an adverse event as treatment emergent unless there is definitive information to determine it is pre-treatment.

All adverse events (including serious adverse events and adverse events of special interest) will be coded to a lower-level term (LLT), preferred term (PT), high-level term (HLT), high-level group term (HLGT), and associated primary system organ class (SOC) using the version of Medical Dictionary for Regulatory Activities (MedDRA) version 20.1. Lower-level term (LLT) will not be presented in the analysis. Number of patients in the SAF will be used as denominator for the percentages calculation.

12.2 Incidence of suicidal ideation (C-SSRS) findings from screening/baseline to the end of the 2-week and the 6-week treatment period and safety follow-up

Patients with a positive response on the C-SSRS (an answer of ‘yes’ to any of the 6 questions) will be described through absolute frequency and percentage at visit 2 (day 14) , visit 3 (day 42) and globally (at any time in the follow-up period) in the study. This percentage will be calculated using the number of patients with C-SSRS evaluation done at the corresponding visit as denominator.

12.3 Incidence of positive psychotic symptoms (BPRS+) findings from screening/baseline to the end of the 2-week and the 6-week treatment period and safety follow-up

The BPRS consists of 4 symptom constructs ((#4, #11, #12, and #15) which ranges from 1 (not present) to 7 (extremely severe). 0 is entered if the item is not assessed. The total score is calculated as the sum of the scores of the 4 items. Incidence of patients with an increase and incidence of patients with a decrease from baseline in the BPRS+ total score will be described at the corresponding visit. Also the change from baseline will be descriptively analysed as a numerical data (see section 7 for further reference) for all patients, for patients with BPRS+ total score reduction and for patients with BPRS+ total score increase.

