# 8.4.1.15.5 Brief Psychiatric Rating Scale Positive Subscale (BPRS+)

The Brief Psychiatric Rating Scale Positive Subscale (BPRS+) will be assessed at screening, visit 2 (day 14), visit 3 (day 42) or early termination, and follow-up visit (28 days after the last IMP administration).

The BPRS is an instrument originally developed to characterize psychopathology and to measure change in clinical psychopharmacology research. It permits the recording of severity of 18 (originally 16) distinct signs and symptoms of psychopathology such as hostility, suspiciousness, hallucination, and grandiosity, based on clinical interview of a patient. It is particularly useful in gauging the efficacy of treatment in patients who have moderate to severe psychoses, and based on the clinician's interview with the patient and observations of the patient's behaviour over the previous 2-3 days. The patient's family can also provide the behaviour report. The rater enters a number for each symptom construct that ranges from 1 (not present) to 7 (extremely severe).

Psychiatric symptoms, associated with PD itself and specifically in patients with Parkinson's psychosis, consist primarily of paranoid delusions, visual hallucinations and/or other sensory disturbances. Psychosis in PD most commonly manifests in visual hallucinations. Auditory hallucinations occur less commonly in PD psychosis (unlike hose seen in schizophrenia) and typically co-occur with visual hallucinations. Tactile, olfactory and gustatory hallucinations have also been reported in PD psychosis and also tend to co-occur with visual hallucinations, but less commonly than other forms of hallucinations. Delusions and is organized thinking are also seen in PD psychosis, although they are not as common as visual hallucinations.

While it is assumed that in this study adverse events known to occur with Bavisant will be directly assessed along with any sleep related effects, the Brief Psychiatric Rating Scale Positive Symptoms Subscale (BPRS+) would be appropriate to observe for psychiatric symptoms occurring in this study, with this population.

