#### BRIEF PSYCHIATRIC RATING SCALE POSITIVE SUBSCALE (BPRS+)

BPRS+ includes just the 4 questions shaded in gray color (#4, #11, #12, and #15)

Please enter the score for the term which best describes the patient's condition. 0 = not assessed, 1 = not present, 2 = very mild, 3 = mild, 4 = moderate, 5 = moderately severe, 6 = severe, 7 = extremely severe

		·	
1. SOMATIC CONCERN Degree of concern over present bodily health. Rate the degree to which physical health is perceived as a problem by the patient, whether complaints have a realistic basis or not.	SCORE	10. HOSTILITY Animosity, contempt, belligerence, disdain for other people outside the interview situation. Rate solely on the basis of the verbal report of feelings and actions of the patient toward others; do not infer hostility from neurotic defenses, anxiety, nor somatic complaints. (Rate attitude toward interviewer under "uncooperativeness").	SCORE
2. ANXIETY Worry, fear, or over-concern for present or future. Rate solely on the basis of verbal report of patient's own subjective experiences. Do not infer anxiety	SCORE	11. SUSPICIOUSNESS Brief (delusional or otherwise) that others have now, or have had in the past, malicious or discriminatory intent toward the patient. On the basis of verbal report, rate only those suspicions which are currently held whether they concern past or present circumstances.	SCORE
3. EMOTIONAL WITHDRAWAL Deficiency in relating to the interviewer and to the interviewer situation. Rate only the degree to which the patient gives the impression of failing to be in emotional contact with other people in the interview situation	SCORE	12. HALLUCINATORY BEHAVIOR Perceptions without normal external stimulus correspondence. Rate only those experiences which are reported to have occurred within the last week and which are described as distinctly different fro	SCORE
4. CONCEPTUAL DISORGANIZATION Degree to which the thought processes are confused, disconnected, or disorganized. Rate on the basis of integration of the verbal products of the patient; do not rate on the basis of patient's subjective impression of his own level of functioning.	SCORE	13. MOTOR RETARDATION Reduction in energy level evidenced in slowed movements. Rate on the basis of observed behavior of the patient only; do not rate on the ba	SCORE

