#### **Instructions for the Clinician:**

The Brief Psychiatric Rating Scale (BPRS) is a widely used instrument for assessing the positive, negative, and affective symptoms of individuals who have psychotic disorders, especially schizophrenia. It has proven particularly valuable for documenting the efficacy of treatment in patients who have moderate to severe disease.

It should be administered by a clinician who is knowledgeable concerning psychotic disorders and able to interpret the constructs used in the assessment. Also considered is the individual's behavior over the previous 2-3 days and this can be reported by the patient's family.

The BPRS consists of 18 symptom constructs and takes 20-30 minutes for the interview and scoring. The rater should enter a number ranging from 1 (not present) to 7 (extremely severe). 0 is entered if the item is not assessed.

First published in 1962 as a 16-construct tool by Drs. John Overall and Donald Gorham, the developers added two additional items, resulting in the 18-item scale used widely today to assess the effectiveness of treatment

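### SAP 9.2.3 scores PDSS-2 as the mirror image of the protocol's key; as a smaller fault, SAP 12.3 has no rule to keep the BPRS+ not-assessed code 0 out of the total

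*SAP*

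**What the plan says.** **PDSS-2.** Protocol 8.4.1.14.3 rates each item from 0 (never) to 4 (very frequent), with a total from 0 (no disturbance) to 60 (maximum disturbance). The form in Appendix 18.6 prints that key. Items 2 to 15 run from 4 for very often down to 0 for never. Item 1, which asks whether the subject slept well, is already printed the other way, from 0 for very often to 4 for never.

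SAP 9.2.3 assigns 0 to very often and 4 to never for every item, reverses item 1 so that very often is 4 and never is 0, and sums the 15 items. It voids the total only when more than 75% of items are missing and describes no proration. SAP 9.1 says which direction is improvement for ESS; SAP 9.2.3 says nothing on this for PDSS-2. SAP 1 says the plan does not alter the protocol's analysis, and SAP 14 lists no changes.

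**BPRS+.** SAP 12.3 rates four items from 1 to 7 and continues: "0 is entered if the item is not assessed. The total score is calculated as the sum of the scores of the 4 items". The protocol form has the same code list ("0 = not assessed, 1 = not present, 2 = very mild"), and its clinician instructions agree: "The rater should enter a number ranging from 1 (not present) to 7 (extremely severe). 0 is entered if the item is not assessed". SAP 12.3 then uses the total as follows: "Incidence of patients with an increase and incidence of patients with a decrease from baseline in the BPRS+ total score will be described". Numerical change is also summarised "for all patients, for patients with BPRS+ total score reduction and for patients with BPRS+ total score increase". The safety baseline is set in SAP 12: "The baseline value is defined as the last available value before the first dose of double-blind IMP taken". Under protocol 8.4.1.15.5 and Appendix 18.15, screening is the only scheduled BPRS+ before dosing.

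**The concern.** PDSS-2 is a secondary efficacy endpoint at weeks 2 and 6, analysed by ANCOVA (SAP 10.2). If the SAP key is programmed and the output is read on the protocol scale, where 60 is worst, a benefit is reported as a worsening and a worsening as a benefit. With no stated direction, nothing in the SAP would alert the reader.

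For BPRS+, 0 is not a severity grade, yet the total is a plain sum and the summary counts any rise or fall. One unrated item can move a subject into the wrong count or out of the right one. Because screening is the only scheduled pre-dose rating, an item left unrated there affects the reference for all three later visits (week 2, week 6 and follow-up).

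**Working it through.** **PDSS-2, complete forms.** Let a_i be the answer to item i, from 0 (very often) to 4 (never).

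- Protocol key (Appendix 18.6): P = a_1 + Σ(4 − a_i), i = 2 to 15.
- SAP key (9.2.3): S = (4 − a_1) + Σ a_i, i = 2 to 15.
- Adding the two: P + S = 4 + 14 × 4 = 60, so S = 60 − P.

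The protocol's stated range is reproduced first:

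| Pattern | Protocol key | SAP key |
|---|---|---|
| No disturbance (a_1 = 0, others 4) | 0 + 14 × 0 = 0 | 4 + 14 × 4 = 60 |
| Maximum disturbance (a_1 = 4, others 0) | 4 + 14 × 4 = 60 | 0 + 14 × 0 = 0 |

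The identity also held on 100,000 random answer sets. For changes, S_2 − S_1 = −(P_2 − P_1): 24 to 20 (−4) becomes 36 to 40 (+4). In a simulated ANCOVA run on X and on 60 − X, the treatment estimate went from −2.41 to +2.41 with the same p-value, 0.0040.

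**Another reading of the reversal.** If the form's printed codes were the input and only item 1 were flipped, no disturbance would score 4 + 0 = 4 and maximum disturbance 0 + 14 × 4 = 56. Neither reading gives the protocol total.

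**PDSS-2, incomplete forms.** The SAP does not say how a partial total is formed; assume that the answered items are summed. With k items answered, S = 4k − P, so the constant differs between visits when k does. Example: P = 24 and S = 36 at baseline; later the answers are the same, but an item worth 2 on both keys is blank. Then P = 22 and S = 34, a change of −2 on both. A blank counts as the best answer on the protocol key and the worst on the SAP key. The threshold permits many blanks: 11 of 15 is 73% and is still scored, while 12 of 15 is 80% and is voided.

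**BPRS+.** Four items rated 1 to 7 give a total from 4 to 28. With at least one 0 in the sum it can run from 0 to 21. Taking the text literally:

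- All items 1 throughout, one unrated after dosing: 4 to 3, a false decrease.
- All items 1 throughout, one unrated at screening: 3 to 4, a false increase at each later visit with all items rated.
- 1,1,1,1 followed by 2,1,1,0: 4 to 4, a real rise hidden.
- The same item unrated at both visits, with the rest unchanged: no error.

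The documents give no rate of unrated items. As an assumption, let each item be unrated independently with probability p at each visit, so blanks are Binomial(4, p) at baseline and at the visit. A false increase in a symptom-free subject needs more blanks at baseline than at the visit; a false decrease is equally likely by symmetry. Counts use the 50 completers per arm in protocol 11.2.

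| p | False increase (same for decrease) | Per 50 | Real one-point rise not counted as an increase |
|---|---|---|---|
| 0.5% | 1.95% | 1.0 | 1.96% |
| 1% | 3.79% | 1.9 | 3.83% |
| 2% | 7.18% | 3.6 | 7.32% |

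**The case against.** The PDSS-2 contradiction is hard to dispute, but its reach can be overstated. A reader might infer that every subject's change is reversed and that the p-value can never move. The documents do not support that: the 75% rule lets incomplete forms be scored, and the partial-form example gives the same sign on both keys. That limit stands.

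On BPRS+ the opposing case is stronger. SAP 12.3 never says outright that the 0 is added, and a not-assessed code need not be read as a score. It can fairly be called an omission, inherited from the plain-sum instruction in protocol Appendix 18.10. But the two statements follow one another and no other rule overrides them: the 75% rules are written for other scales. The consequence is modest. SAP 12 states: "The analysis of the safety variables will be essentially descriptive and no systematic testing is planned". Raters are trained (protocol 8.4.1.15.6) and missing values are queried (16.2.1), which makes blanks less likely but need not catch a permitted 0. Independence of items is also an assumption; clustered blanks would touch fewer subjects.

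Two further inferences should be resisted. One is that SAP 12.3 leaves the percentage denominator undefined. It names none, but SAP 7 excludes missing data from percentages throughout, so that is not a fault. The other is that arms would be biased on BPRS+. If items are unrated at random, no between-arm difference is expected.

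**Conclusion.** The PDSS-2 key in SAP 9.2.3 contradicts the protocol text and form on all 15 items and should be corrected. For complete forms the result is exact: 60 minus the protocol total, opposite sign for changes, estimate and confidence interval, same p-value. This needs no assumption about the data. For incomplete forms the distortion is real but is not a pure mirror image. As the SAP declares no departure from the protocol, this is best read as an unintended coding error.

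The BPRS+ gap is secondary. Followed literally, the text produces false and hidden cases in small descriptive counts and wrong values in the increase and reduction subgroups. Its size rests on assumed unrated-item rates: at 0.5% to 2%, about 1 to 4 of 50 completers per arm in each direction per visit. The primary ESS analysis is unaffected by either fault.

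**What to change.** **SAP 9.2.3.** Replace the scoring text with: *Items 2 to 15: 0 = Never to 4 = Very often. Item 1: 0 = Very often to 4 = Never, as printed on the form, with no further reversal. Total from 0 (no disturbance) to 60 (maximum disturbance); negative change means improvement. Missing items are not counted as 0: the total is computed only from complete forms, or prorated under a stated threshold.* The key change loses no data. Restricting totals to complete forms would lose partial ones; proration would keep those within the threshold.

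**SAP 12.3.** Add: *Code 0 is set to missing. The BPRS+ total, its change and the increase and decrease flags are computed only when all four items are rated 1 to 7 at both baseline and the visit. The number not evaluable is shown by visit and arm. The rated items of these subjects are listed, with any item above its baseline rating marked.*

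This costs SAP wording and derivation code. Under the same assumed rates the share not evaluable at a visit is 1 − (1 − p)^8, which is 3.93%, 7.73% or 14.92%, or 2.0, 3.9 or 7.5 of 50 per arm. That is about twice the share of real one-point rises that the literal rule would miss. Some subjects with a real rise therefore move from the count to the listing, which is why the listing belongs in the rule. Complete-case scoring is a choice, not the only possible correction.
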